3.5.2 Study Design/Recruitment Considerations Related to Age Groups

The study design and recruitment strategy aim to achieve representation of age groups that reflect the demographics of the affected population. This includes adults aged 18 or older. GI cancers occur at any age but mostly in patients aged 60 or older. To maximize the generalizability of results,

Pilot Study - Ketamine Page 21 of 55

enrollment should reflect the age distribution of the affected population who is likely to use the investigational drug(s) in clinical practice.

3.6 Duration of Treatment

Ketamine treatment will be given on Day 0. K-MaP therapy will continue from Day -13 to Day 14 (about 28 days) or until:

- Inter-current illness that prevents further administration of treatment;
- Unacceptable adverse event(s);
- Participant decides to withdraw from the study;
- Significant participant non-compliance with protocol;
- If the participant meets an exclusion criterion (either newly developed or not previously recognized) that precludes further study participation
- General or specific changes in the participant's condition render the participant unacceptable for further treatment in the judgment of the investigator.

3.7 Duration of Follow Up

Participants will be followed for 35 days (+/- 2 days) after treatment with ketamine (on Day 0/Visit 4) or removal from the study, whichever occurs first. Participants removed from the study for unacceptable treatment- or study-related adverse event(s) will be followed until resolution or stabilization (as determined by the investigator), whichever occurs first.

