2.3 Secondary Objectives and Endpoints

Secondary Objective	Endpoint(s)	Time Frame

Pilot Study - Ketamine Page 15 of 55

1.	To characterize the preliminary safety and tolerability of K-MaP in patients with stage 3 and 4 GI cancers.	 Adverse events (AEs), Unexpected AEs, and Serious AEs, by CTCAE (v.5.0). Vital signs (heart rate and blood pressure) Patient-reported outcome: challenging experiences (CEQ) 	 Day -28 through Day 35. Day 0 (multiple time points on day of ketamine administratio n). Day 0, 3-4 hours after ketamine administratio n.
2.	To assess the magnitude and durability of improvement from randomization in psychosocial distress.	 Clinician-rated outcomes: Global clinical impression of severity(CGI-S), Demoralization (DI), Mood symptoms (GRID-HAMD-6). Patient-reported outcomes: Demoralization (DS-II), Depression (PHQ9), Anxiety (GAD7), Quality of Life (FACIT-PaI-14). 	From Day -28 to Day 35.
3.	To assess the magnitude and durability of improvement from randomization in pain.	Patient-reported outcome: pain (BPI-SF)	From Day -28 to Day 35.
4.	To assess the magnitude of change from randomization in opioid analgesic use.	Patient-reported outcome: Opioid use (<24hr morphine milligram equivalence [MME])	From Day -28 to Day 35.
5.	To assess the magnitude of change from randomization in interoceptive awareness.	Patient-reported outcome: interoceptive awareness (MAIA-2)	From Day 0 to Day 7

Pilot Study - Ketamine Page 16 of 55

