7.3 Prohibited Medications

The medications below may not be used during the study. If participants require these medications, they will be taken off-study (except for when anxiolytics as rescue medications ar used during the ketamine medication visit on Day 0/Visit 4).

- Anxiolytics, as needed
- Lithium

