8.4 Expedited Reporting

8.4.1 Reporting to the HDFCCC Data and Safety Monitoring Committee

If a death occurs during the treatment phase of the study or within 30 days after the last administration of the study drug(s) and it is determined to be related either to the study drug(s) or to a study procedure, the UCSF PI or his/her designee must notify the DSMC Chair (or qualified alternate) within 1 business day of knowledge of the event. The contact may be by phone or e-mail.

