8.5 Follow-up of Adverse Events

All participants who experience adverse events will be followed with appropriate medical management until resolved or stabilized, as determined by the investigator. For selected adverse events for which administration of the study drug/intervention was stopped, a re-challenge of the subject with the study drug/intervention may be conducted if considered both safe and ethical by the investigator.

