9.1 Sample Size Considerations

9.1.1 Sample Size and Power Estimate

No formal power analysis was conducted, and no formal tests of efficacy will be conducted. This N=12 pilot study has a sample size sufficient for assessing the feasibility and preliminary safety of a novel behavioral-pharmaceutical intervention, at two different dose levels and routes of administration of the study drug.

If the 0.5mg/kg PO dose of ketamine is well-tolerated (i.e., zero treatment-related SAEs) and demonstrates mean clinical improvement in demoralization assessed by DS-II that endures beyond 7 days post-drug, then this would suggest a fully powered study is warranted using the 0.5mg/kg PO dose.

If the 0.5mg/kg IM dose of ketamine is well-tolerated (i.e., zero treatment-related SAEs) and demonstrates mean clinical improvement in demoralization assessed by DS-II that endures beyond 7 days post-drug, then this would suggest a fully powered study is warranted using the 0.5mg/kg IM dose.

If the either dose is well-tolerated and fails to demonstrate mean clinical improvement in demoralization assessed by DS-II that endures beyond 7 days post-drug, then this would suggest that the dose is an appropriate control for other psychoactive investigational drugs whose clinical effects are expected to have greater durability.

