3.2 Serious Adverse Event Reporting

By definition, an adverse event is defined as a serious adverse event (SAE) according to the following criteria:

- Death.
- Life-threatening adverse experience*,
- Inpatient hospitalization or prolongation of existing hospitalization,
- Persistent or significant disability/incapacity,
- Congenital anomaly/birth defect, or cancer, or
- Any other experience that suggests a significant hazard, contraindication, side effect or precaution that may require medical or surgical intervention to prevent one of the outcomes listed above,
- Event that changes the risk/benefit ratio of the study.
- * A life-threatening adverse experience is any AE that places the patient or subject, in the view of the investigator, at immediate risk of death from the reaction as it occurred, i.e., it does not include a reaction that, had it occurred in a more severe form, might have caused death.

Serious adverse event reporting will be in accordance with all IRB regulations. For trials conducted under an investigational new drug (IND) application, the SAE will be reported in accordance with Code of Federal Regulation Title 21 Part 312.32 and will be reported on a Med Watch form.

UCSF IRB website for guidance in reporting serious adverse events:

https://irb.ucsf.edu/adverse-event

Med Watch forms and information:

www.fda.gov/medwatch/getforms.htm

Pilot Study - Ketamine Page 54 of 55

All serious adverse events are entered into OnCore, as well as submitted to the IRB (per IRB guidelines). The SAEs are reviewed and monitored by the Data and Safety Monitoring Committee on an ongoing basis and discussed at DSMC meetings, which take place every six weeks. The date the SAE is sent to all required reporting agencies will be documented in OnCore®.

If the SAE involves a subject death, and is determined to be possibly, probably or definitely related to the investigational drug or any research related procedure, the event must be reported to the DSMC Chair (or Vice Chair) and DSMC Director within one business day.

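### Section 3.7 can be read as ending a dosed participant's follow-up at removal, which conflicts with the Day 35 safety endpoint and leaves the zero-SAE criterion open to incomplete observation

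*Combined protocol and SAP*

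**What the plan says.** **Length of follow-up.** Section 3.7 sets 35 days (+/- 2) after ketamine "or removal from the study, whichever occurs first". It then adds an extension: "Participants removed from the study for unacceptable treatment- or study-related adverse event(s) will be followed until resolution or stabilization". Section 8.5 has a similar rule for events that have occurred: "All participants who experience adverse events will be followed with appropriate medical management until resolved or stabilized".

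**Safety endpoint and population.** Section 2.3 gives the time frame for AEs, unexpected AEs and SAEs as "Day -28 through Day 35", with no exception for removed participants. Section 7.4 bases the safety analysis on everyone who receives ketamine.

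**Leaving the study.** Section 7.3 covers as-needed anxiolytics and lithium: "If participants require these medications, they will be taken off-study". Anxiolytics given as rescue at the Day 0 visit are exempt. Section 3.3.1, item 8, has the same consequence for a longer list that adds lamotrigine, clozapine and dopamine agonists.

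**Reporting.** Section 8.4.1 requires prompt notice to the DSMC Chair of a related death during treatment or in the 30 days after the last dose. Appendix 2, Section 3.2, says "All serious adverse events are entered into OnCore, as well as submitted to the IRB", with no time limit.

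**Use of the result.** Section 9.1.1 treats a dose as "well-tolerated (i.e., zero treatment-related SAEs" and uses that in each of its three rules on what to do next with a dose. Section 9.2.3 repeats the zero-SAE criterion.

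**The concern.** A criterion of zero events is only as good as the search for events. An SAE that nobody looks for counts the same as one that did not happen, so incomplete observation can push the tolerability result in one direction only, towards a pass. The plan sets no minimum observation time, no rule for dosed participants not seen to Day 35, and no denominator of observed time.

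Removal may also be informative. A participant who comes to need an as-needed anxiolytic or lithium after dosing may be one whose mental state has worsened. If that need is not itself classed as an unacceptable related AE, the extension in Section 3.7 does not apply. The scheduled AE and C-SSRS checks could then stop for that participant.

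Two things are at stake: safety surveillance of dosed people in a frail population, and a per-arm tolerability call in six patients that feeds a decision about a fully powered study. This concerns the finding of adverse events. It is separate from missing questionnaire scores and the exit interview.

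**Working it through.** The plan gives no power figure, SAE rate, removal rate or operating characteristic for the zero-SAE criterion, so there is no stated figure to reproduce. The check has two parts.

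**1. Do the sections fit together?**

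| Provision | Covers a new non-fatal SAE after removal? |
|---|---|
| 2.3, 7.4 | Implied by the Day 35 time frame and all-dosed set; no procedure given |
| 3.7, main rule | Not if follow-up stops at removal |
| 3.7 extension; 8.5 | Known events only |
| 6.1 Study Calendar | AEs and C-SSRS at scheduled visits; no early-termination visit or contact after removal |
| Section 5, contact number given after dosing | Passive; depends on participant or caregiver calling |
| 8.4.1 | Related deaths only, once known |
| Appendix 2, 3.2 | All SAEs, once known |

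The endpoint and analysis set assume Day 35 data on everyone dosed. No section sets out how those data are obtained after removal.

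**2. How much could it matter?**

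Inputs from the plan: 6 participants per arm (abstract, Sample Size) and 35 post-dose days (3.7). Assumed, because the documents are silent: the true 35-day risk *p* of a treatment-related SAE, the number *k* removed, removal on Day 7, and no ascertainment afterwards.

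*Observation time.*
- Full observation: 6 × 35 = 210 person-days per arm.
- One Day 7 removal loses 35 − 7 = 28 days; 28/210 = 13%.
- Two lose 56 days; 56/210 = 27%, leaving 154.

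*Chance of zero related SAEs in an arm.*
- Full observation: (1 − p)^6.
- With *k* removed on Day 7 and constant hazard: (1 − p)^(6 − k) × (1 − p)^(k × 7/35). For k = 2 the exponent is 4 + 2 × 0.2 = 4.4.

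| Assumed p | Full: (1 − p)^6 | Two removed on Day 7: (1 − p)^4.4 |
|---|---|---|
| 5% | 73.5% | 79.8% |
| 10% | 53.1% | 62.9% |
| 20% | 26.2% | 37.5% |
| 30% | 11.8% | 20.8% |

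With one removal on Day 7 at p = 10%, the chance is 57.8%.

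*Sensitivity to timing.* Let *f* be the share of the 35-day cumulative hazard that falls by Day 7. With two removals the exponent is 4 + 2f. At p = 10%:
- f = 1 (all risk early): 0.9^6 = 53.1%, no effect.
- f = 0.2 (constant hazard): 62.9%.
- f = 0 (all risk late): 0.9^4 = 65.6%.

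These figures give removed participants the same risk as the others. If they are at higher risk, the effect is larger.

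*For scale.* With complete observation and 0 of 6, the exact 95% upper bound on the true risk is 1 − 0.05^(1/6) = 39.3% one-sided, or 1 − 0.025^(1/6) = 45.9% two-sided.

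**The case against.** The strongest reply is that Section 3.7 need not mean what it appears to mean. Removal can be read as an alternative starting point for the 35 days. A dosed participant receives ketamine before any later removal, so follow-up would then run to Day 35 in any case. That reading agrees with the abstract, which gives up to 35 days after ketamine and does not mention removal, and with Sections 2.3 and 7.4. This stands. A reader might infer that safety observation definitely ends at removal and that later SAEs go uncounted. The documents do not support so firm a statement: Appendix 2 has all SAEs entered, without a time limit.

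Three further stronger inferences also fail:

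- **Every ground in Section 3.6 is a removal ground.** That section concerns duration of treatment. Intercurrent illness and a change in condition are worded as reasons to stop treatment and are not said to end study participation. The clear post-dose routes out are a prohibited medication, the participant's withdrawal, and an exclusion criterion that precludes further participation.
- **Section 8.4.1 sets a 30-day surveillance window.** It covers expedited notice of deaths judged related and no other events.
- **Lost days equal lost risk.** Ketamine is a single dose whose effects begin to wear off at 1.5-2 hours (Section 5). Under Section 8.2.2, a late event more likely due to the cancer would be unrelated and would not count. Constant hazard may therefore overstate the effect.

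It is also fair that Section 9.1.1 only says a result would suggest a larger study, and that the two rules supporting one also require DS-II improvement. The bias is modest beside the imprecision of six patients. None of this supplies a contact after removal or a completeness condition on the criterion.

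**Conclusion.** The point holds as a conflict between sections and an ascertainment gap on one plausible reading. Section 3.7 can be taken to stop follow-up of a dosed participant at removal, which does not fit the Day 35 endpoint in 2.3 or the all-dosed safety set in 7.4. On that reading, new non-fatal SAEs after removal may not be found, and the zero-SAE criterion can only gain from the loss.

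The size cannot be established from the documents. With two of six removed on Day 7, assumed risks of 5% to 30% and constant hazard, the chance of zero SAEs rises by 6 to 11 percentage points (79.8 − 73.5 = 6.3 at 5%; 37.5 − 26.2 = 11.3 at 20%). The rise is smaller if risk falls soon after dosing and larger if removed participants are at higher risk. Unlike the imprecision of n = 6, this source of error is cheap to avoid, so the change should be made.

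**What to change.** In Section 3.7, reconcile the follow-up rule with Sections 2.3 and 7.4. State that stopping treatment or being taken off study does not end safety observation. State also that AEs and SAEs are collected to Day 35, by phone or record review, for every dosed participant who has not withdrawn consent to it, whatever the reason for leaving.

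In Section 9.2.3, report by arm the number observed to Day 35, or the observed post-dose days, beside the SAE count, so that a zero can be read against the observation behind it.

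The cost is protocol wording plus a few calls or record checks per removed participant. The change affects data collection only.

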3.8 Randomization Procedures

A total of 12 patients will be randomized on Day 0 at a 1:1 ratio to receive either 0.5 mg/kg of oral ketamine, or 0.5 mg/kg of IM ketamine. Randomization will be in block sizes of 4.

3.9 Primary Completion

Each individual will participate for at least 7 weeks (Day 35) plus [up to 4 weeks] from telephone screening to the baseline study visit (between Day -28 to -7). The expected primary completion date for a sample of 12 participants is 1.5 years after the study opens to accrual.

3.10 Study Completion

The expected on-study completion date is 1.5 years after the study opens to accrual.

4 Investigational Products

4.1 Description, Supply and Storage of Investigational Products

4.1.1 Ketamine

Classification

NMDA-receptor antagonist

Mechanism of Action

Ketamine is a nonselective, noncompetitive N-methyl-D-aspartate (NMDA) receptor antagonist. The mechanism by which it exerts its antidepressant effect is unknown; a transient dissociative experience correlates with better depression outcomes. The major circulating metabolite norketamine demonstrated activity at the same receptor with less affinity.

Pilot Study - Ketamine Page 22 of 55

Metabolism

Substrate of CYP2B6 (major), CYP2C19 (minor), CYP2C9 (minor), CYP3A4 (minor). Note: assignment of major vs. minor substrate states are based on clinically relevant drug interaction potential

Contraindications

Hypersensitivity to esketamine, ketamine, or any component of the formulation; aneurysmal vascular disease (including thoracic and abdominal aorta, intracranial, and peripheral arterial vessels) or arteriovenous malformation; history of intracerebral hemorrhage

Formulation, Appearance, Packaging, and Labeling

This study will use commercially available (non-diluted) ketamine (ideally, 50mg/mL - NDC 42023-114-10, manufactured by Par Pharmaceutical). However, if not available due to market inventory, we will substitute with a generic alternative or different concentration of commercially available product (i.e., ketamine 50mg/mL - NDC 0143-9508-10, manufactured by Hikma; ketamine 50mg/mL - NDC 55150-439-10, manufactured by AuroMedics Pharmaceuticals; ketamine 10mg/mL - NDC 42023-113-10, manufactured by Par Pharmaceutical; ketamine 10mg/mL - NDC 55150-438-10, manufactured by Par Pharmaceutical; ketamine 100mg/mL - NDC 0143-9509-10, manufactured by Hikma; or ketamine 100mg/mL - NDC - 55150-440-10, manufactured by AuroMedics Pharmaceuticals). Review the FDA approved package labeling for ketamine for more information.

Availability

Ketamine (Ketalar) is an FDA approved product. We will purchase it from AmerisourceBergen, a commercial distributor. If the Par Pharmaceutical formulation is not available, we will substitute with one of the other formulations available , as described above.

Storage and handling

Store at 20° to 25°C (68° to 77°F). Protect from light. Review the FDA approved package labeling for ketamine (Ketalar) for more information.

Side Effects

Complete and updated adverse event information is available in the FDA approved package labeling for ketamine (Ketalar).

4.2 Accountability Records for Investigational Product(s)

The Principal Investigator and research team will be responsible for managing investigational product accountability records, including inventory logs, transfer forms, and usage logs in compliance with the UCSF Controlled Substances Program Manual:

After consulting with the UCSF Investigational Drug Service, it was determined that they will not be engaged in this trial due to the non-General Acute Care Hospital (GACH) setting of the study site.

4.3 Ordering Investigational Product

The Principal Investigator will obtain ketamine (Ketalar) directly from a commercial distributor, AmerisourceBergen. If not available through the commercial distributor due to inventory issues, the Principal Investigator has received approval from the Director of the Investigational Drug Pharmacy

Pilot Study - Ketamine Page 23 of 55

Services at UCSF Health to obtain ketamine (Ketalar) through a transfer from the UCSF Parnassus Pharmacy as a DEA coincident activity for research purposes.

5 Treatment Plan

K-MaP will consist of 4 sessions of Meaning and Purpose (MaP) therapy and a single dose of ketamine on day 0. Two MaP sessions will occur prior to ketamine therapy, the 1st session between days -13 and -7, and the second session between days -12 to -1. The two sessions of MaP after ketamine administration will occur on days 3 (+/- 2 days) and 11 (+/- 3 days). MaP sessions may occur in-person at UCSF or via telehealth; however, we will strongly recommend that participants undergo at least one of the first two MaP sessions in-person when doing so is logistically feasible.

MaP is a manualized existential behavioral intervention, in which participants discuss their condition, their thoughts and feelings about their health and life, and are prompted to explore what brings meaning to their life. All MaP sessions and the ketamine administration visits will be video- and audio-recorded on a camcorder with a removable storage chip or PHI-compliant software (i.e., Zoom). The recordings on the chips will be downloaded onto encrypted external hard drives. The camcorders, chips, and hard drives will be stored in locked cabinets in a secure and locked room. The recordings will be securely uploaded to a dedicated UCSF Research Analysis Environment (RAE) workspace for analysis at a later date. Transcripts of recordings will be analyzed to assess treatment fidelity and qualitative assessment of the participant's subjective experiences. MaP sessions will not be billed to participants or their insurance.

After two MaP sessions, participants will receive ketamine on Day 0. This session will last about 4 hours. Participants will arrive to the Neurosciences Clinical Research Unit (NCRU) of the Sandler Building at UCSF Mission Bay, where they will be oriented to the treatment room for this study, which will contain a couch or bed for the participant to lie on in a private setting. Participants will hand over their shoes, keys, wallet, and phone to the study clinicians for safekeeping; these will all be returned to the participant upon completion of the treatment session. They will then complete all prerandomization assessments described in Section 6 of this study protocol. The ketamine session will be audio and video recorded, but participants will have the option of requesting that the recording be paused momentarily if they wish to discuss matters that are too personal to be recorded. There will be an on-site study physician (MD or DO) with 1) experience in the management of psychiatric emergencies and 2) experience or certification in the management of cardiovascular emergencies. Ketamine, its administration, and the medication visit will be paid for by the study and will not be billed to participants or their insurance.

Pilot Study - Ketamine Page 24 of 55

During the medication session, vital signs (heart rate and blood pressure) will be recorded at 10 minutes prior to ingestion of the oral solution ("Minute -10"), and then 30, 60, 90, 120, and 180 minutes after oral ingestion. If at 180 minutes blood pressure is meaningfully elevated compared to Minute -10, blood pressure will continue to be repeatedly assessed until it has returned to near its Minute -10 measurement. Respiratory rate and oxygen saturation will be assessed as needed.

In the event of elevated blood pressure prior to study drug administration

If the Minute -10 assessment (the mean of at least two readings separated by at least 2 minutes) of blood pressure exceeds either 140 systolic or 90 diastolic, periodic blood pressure readings will be obtained (e.g. at 5-minute intervals) to determine if the elevation may be temporary (e.g. due to anticipatory anxiety). If blood pressure decreases to (or below) 140 systolic and 90 diastolic within 20 minutes, study drug administration will proceed.

If blood pressure continues to exceed either 140 systolic or 90 diastolic, periodic blood pressure readings will be continued, and the study physician will be contacted. The study physician can authorize study drug administration if the study physician believes that it is safe to proceed and if the last two blood pressure readings do not exceed 155 systolic or 95 diastolic. The determination that it is safe to proceed requires that 1) the participant endorses currently feeling anxiety, 2) the participant is <70 years of age, 3) the participant's medical history is negative for stroke, myocardial infarction, heart failure, flash pulmonary edema. The study physician must regularly care for patients with serious medical illness and/or in acute care settings.

The participant will be randomized to ingest liquid ketamine 0.5mg/kg vs. an equivalent mL quantity of normal saline (placebo) mixed with cranberry juice (prepared by unblinded study staff) in a medication administration room located next door to the treatment room. At 10 minutes following oral ingestion of cranberry juice, while sitting in a wheelchair in the medication administration room, all participants will be administered an intramuscular injection (also prepared by unblinded study staff). The injection will be administered either by an RN, NP, or MD/DO involved in the study. Participants who received oral ketamine 0.5mg/kg will be administered normal saline via IM injection while those who received normal saline (placebo) in cranberry juice will receive ketamine 0.5 mg/kg IM. Following this injection, the participant (still in a wheelchair) will be rolled into the treatment room located across the hall from the medication administration room, where they will be supported by the therapy facilitators in transferring from the wheelchair to the couch and instructed to lie down wearing eyeshades and listening to a preselected music playlist via headphones or speakers. The participant will be instructed to focus their attention internally and to attempt to interact minimally with the two facilitators present in the room throughout the drug session. The facilitators will be as nondirective as possible in their interactions with the participant. In the event of a psychologically challenging experience such as significant anxiety or confusion, the facilitators will provide verbal reassurance and, when consented to prior to the session, supportive touch (e.g., brief handholding or hand-on-shoulder). Participants will have been instructed in the preparatory therapy session to notify the study therapists if during the treatment they feel anxiety or fear.

Facilitators will work in dyads (one Lead Facilitator and one Assistant Facilitator) and have licensure or clinical experience according to the following requirements, which the FDA has used for prior studies of medication-assisted talk therapy:

Lead Facilitator: Licensed to provide healthcare with professional training and clinical experience in psychotherapy. They must be licensed to practice independently. Acceptable professional credentials are limited to the following: clinical or counseling psychologist (PhD or PsyD), psychiatrist or other

Pilot Study - Ketamine Page 25 of 55

physician (MD or DO), Master of Social Work (MSW), masters Licensed Clinical Professional Counselor (PCPC), or licensed Psychiatric Nurse Practitioner (Psychiatric NP).

Assistant Facilitator: Must have at least a bachelor's degree and at least one year of clinical experience in a licensed healthcare setting. Their clinical experience may have been in medical care, mental health care, or professional spiritual care (aka, chaplaincy).

In the event of a psychiatric emergency, verbal de-escalation and physical and/or chemical restraint will be used to maintain the safety of the participant and the facilitators, according to the clinical judgment of the on-call study physician. All reasonable efforts will be made to avoid using restraints of any kind. Participants will not be allowed to leave the premises until the drug effects have worn off.

In the event of a medical emergency, participants will be evaluated by the on-call study physician. At least one ACLS-certified study clinician will be on-site for all drug administrations. While expected to be rare, the most likely non-psychiatric serious adverse event to occur would be a hypertensive crisis. If a participant's blood pressure becomes grossly elevated (SBP >180mmHg, DBP >110mmHG) or unsafe (BP elevations with associated symptoms such as chest pain or shortness of breath), blood pressure will be rechecked immediately in both arms and the on-call physician will be notified if s/he is not already in the treatment room. If the participant is clinically suspected of being in hypertensive emergency (with signs of end-organ damage), then the participant will be transported to the nearest Emergency Department for further evaluation and treatment. If the participant is determined to be in hypertensive urgency (without clinical signs of end-organ damage), then blood pressure will be reassessed with greater frequency while the study physician continues her/his evaluation for signs of clinical instability, and the study staff may attempt to calm the participant with verbal de-escalation, a short-acting blood pressure medication (e.g. clonidine), or an anxiolytic (e.g. lorazepam), as transient hypertension is often due to a challenging psychological experience. If after 30 minutes, the hypertensive urgency has not improved, the study physician will evaluate the need for transporting the participant to the Emergency Department for further evaluation and treatment.

In the case of acute chest pain, the on-call study physician will have available sublingual nitroglycerin to administer to the participant. An automated external defibrillator (AED) will be located in the building, but the goal will be to transport a decompensating patient to the Emergency Department prior to an AED becoming necessary.

As the drug effects begin to wear off at the 1.5-2-hour mark, the facilitators will engage the participant in a therapeutic interview (also video-recorded) to explore the experience. Patient-reported outcomes characterizing the Ketamine experience—the Mystical Experience Questionnaire (MEQ) and the Challenging Experience Questionnaire (CEQ)—will be obtained. Trained study staff will administer the Columbia suicidality rating scale (C-SSRS) and the Heartbeat Detection (HBD) task. Only once participants are deemed to be free of the acute effects of ketamine, and after at least 3 hours have passed since ingestion of ketamine, will the participant be allowed to leave the premises in the company of a caregiver who has been instructed on how best to support the participant over the coming days.

The participant and caregiver will be given a study clinician's pager or work cell phone number in case of any clinical event off-site that needs further assessment. Participants must agree not to drive themselves home nor to drive later that same day after they arrive home. Participants will be instructed to write a detailed account of their experience as soon as possible over the following week.

Participants will be reminded well before the day of ketamine administration that a caregiver will need to take them to and from the 4-5-hour appointment. In the event that a participant did not arrange a friend/family member to accompany them home, the participant will be required to stay with the study

Pilot Study - Ketamine Page 26 of 55

staff, will be encouraged to eat, and then the participant will be escorted outside by a study team member who will accompany the participant home in a taxi/Lyft/Uber. The taxi/Lyft/Uber fee will be paid for by the study.

